### • Follow-up of Adverse Events

Adverse events should be followed up to determine the outcome.

AEs that are serious or severe or considered related to the study medication or study procedures must be followed up by the investigator until the AE is resolved or resolved with sequelae, and until all queries related to the AE have been clarified. If the subject had an AE with fatal outcome, an autopsy report should be provided if possible.

If AEs that are serious or severe or considered related to study medication or study procedures are ongoing at the time of the subject's last study visit, or if the subject has clinically relevant laboratory parameter abnormalities at the last study visit, one or more safety follow-up visit should be scheduled for those subjects. The investigator should set the interval to the additional Safety follow-up visit according to his/her medical judgment. Follow-up activities should be continued until the investigator considers it medically justifiable to stop further follow-up.

All other AEs must be followed up by the investigator until the AE is resolved or resolved with sequelae or the end of the period of observation (= last study visit), whichever comes first.

The investigator should respond to any queries raised by the sponsor in relation to adverse events, including provision of supporting documentation for SAEs or other IRAEs (e.g. ECG data, laboratory results, hospital summary, autopsy report) within the requested timeline. In case of fatal or life-threatening SAEs the sponsor may request urgent clarification within one calendar day. In general, if for AEs requiring immediate reporting from investigator to sponsor (IRAE/SAE) follow-up information becomes available, this must be reported to the sponsor **within 24 h** of becoming aware of this information (i.e. the same timeframe as for initial IRAE/SAE reports). Any supporting documents have to be identified by the patient number, and personal data (e.g. subject name, address or phone number) obliterated prior to sending to the sponsor. For details on reporting IRAE/SAE see section 14.6.4.

Adverse event data in the CRF must be updated accordingly when follow-up information is received.

All efforts to collect follow-up information must be documented in the subject's source data.

Subjects who were treated with the study medication but did not complete the study as per protocol, should receive all the examinations and investigations scheduled for the last study visit. The investigator should make all efforts to contact subjects lost to follow-up and document the attempts in the subject's source data.

### 14.6.2.2 Responsibilities of Sponsor

For purposes of safety analyses all AEs will be recorded in the clinical database. To ensure the basis for expedited and periodic notification of authorities, IRAEs will be additionally recorded in the drug safety database of the sponsor.

### 14.6.3 Evaluation of Adverse Events

#### 14.6.3.1 Responsibilities of Investigator

To permit standardized assessment of AEs, the investigator will evaluate amongst others the seriousness, severity and causality of each AE using the AE pages of the eCRF.

The seriousness, severity and causality of each AE will be evaluated by the investigator in accordance with the definitions in **section 14.6.1**.

#### Causality of AE:

For all AEs a causality assessment must be provided, even if based on preliminary data, and documented on AE page of the eCRF.

### 14.6.3.2 Responsibilities of Sponsor

The causality assessment given by the investigator will not be downgraded by the sponsor. If the sponsor disagrees with the investigator's causality assessment, both the opinion of the investigator and the sponsor will be recorded.

### 14.6.4 Notifying of Adverse Events

### 14.6.4.1 Responsibilities of Investigator

In this study AEs will be reported electronically from the site to the sponsor using the eCRF.

All known information regarding IRAEs (SAEs, AESIs, pregnancy, and AEs leading to withdrawal) must be recorded on the AE log of the eCRF **within 24 hours** of the site learning of the event (see also section 14.6.2.1).

In case the electronic system is not function 24 hours, SAE paper forms will be provided to be used in the case of an IRAE. The paper forms will also need to be faxed or e-mailed to the sponsor within 24 hours of the site learning of the AE.

#### Adverse Event Reporting Contact:

For questions regarding IRAEs, or to provide information that cannot be provided electronically via the eCRF, or to notify the sponsor of an IRAE in the event of technical failure, the investigator should contact:

# 14.6.4.2 Responsibilities of Sponsor

Biotest's Corporate Drug Safety department is responsible for fulfilling all obligations regarding notification of Regulatory Authorities and IECs/ IRBs according to applicable regulatory requirements (expedited and periodic reporting, e.g. serious unexpected suspected adverse reactions, Development Safety Update Report). In addition, the sponsor will be responsible for information of investigators according to the current legislation.

# 14.6.4.3 Pregnancy Reporting

In the unlikely event that a woman becomes pregnant during the study this is reported within 24 hours of the site learning of the situation using the "Drug Exposure via Parent Report Form" paper form and the contact details as above. The investigator should make any reasonable effort to follow-up the pregnancy until birth of the child; and will report all outcomes associated with the pregnancy to the sponsor.

# 14.6.4.4 Investigational Product Complaints

Complaints associated with the investigational medicinal product must be recorded in the eCRF and reported to the sponsor **within 24 hours** of the investigator becoming aware of the IMP complaint, using the "Investigational Medicinal Product Complaint" report form. In case of corresponding AEs related to suspected quality defects, the AEs have to be entered in the respective eCRF pages (AE page/ IRAE page).

Any complaint samples should be provided to the sponsor upon request.

# **15 STATISTICS**

The statistical planning and evaluation of the study will be carried out by a qualified statistician in accordance with the ICH-guidelines and adequate biostatistical SOPs. A detailed Statistical Analysis Plan (SAP) will be prepared at the latest before data base lock.

## 15.1 Calculation of Sample Size

The primary objectives of this study are key PK parameters. For the PK parameters no formal sample size calculation is carried out. As a general rule approximately 20 patients in this single cohort should suffice to calculate PK parameters with the corresponding range of distribution.

For the surrogate (secondary) efficacy variable MCF (maximal clot firmness), a formal sample size calculation was performed.

On the basis of a t-test assessing the difference between dependent means (postminus pre-treatment MCF difference; one sample) the sample size can be calculated.

The mean MCF in the study population consisting of patients with congenital fibrinogen deficiency (i.e., a- or severe hypofibrinogenemia) prior to BT524 treatment and 1 hour after treatment will be measured by Fib-tem S of ROTEM.

With 15 patients, a pre-treatment mean of 4 mm (SD 7 mm) and a post-treatment mean of 10 mm (SD 8 mm) an effect size of 0.8 mm can be detected with a power of 80% at  $\alpha$  = 0.05 (2-sided) significance level.

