Criteria (continued)	
 
In addition to the general exclusion criteria mentioned above, patients meeting any of the following PK-specific exclusion criteria at enrolment are to be excluded from the pharmacokinetic assessment. Patient enrolment is to be postponed until no PK exclusion criterion applies.
 
20. Elective surgery during the 14 day PK blood sampling period
 
21. Acute infection
 
22. Clinically relevant increase or decrease in body temperature
 
23. Actively bleeding or anticipated bleeding (including female menorrhea) at the time point of or within 7 days prior to infusion of BT524
 
24. Surgery within 7 days prior to infusion of BT524
 
25. Immobilization within 7 days prior to infusion of BT524
 
26. Intake of alcohol or significantly increased intake of caffeine containing products within 24 hours prior to infusion of BT524
 
27. Blood donation or comparable blood loss within 60 days prior to infusion of BT524
 
28. Excessive physical exercise (extreme sports activities, sauna) within 72 hours prior to infusion of BT524
 

Number of Study Patients	Part I Approximately 20 patients ≥ 6 to ≤ 75 years will be included to have about 15 evaluable patients for the analyses of the PK/PD of BT524 and the surrogate efficacy parameter. At least 3 additional patients 0 to < 6 years of age are to be included to have 3 evaluable datasets for PK/PD assessment.
	Part II At best, all patients who have completed part I will continue with the extended on-demand prophylaxis (ODP)/ on-demand treatment (ODT).
	Subsequent to completion of part I by the first 20 subjects $\ge 6$ to $\le 75$ years, at least 10 additional patients and at least 3 additional patients < 6 years will be treated in part II without PK/PD assessments in part I.
	In total, approximately 36 patients 0 to $\leq$ 75 years should be treated in part II. Thereof, at least 6 patients should be < 6 years, 6 patients should be $\geq$ 6 to < 12 years and 6 patients should be $\geq$ 12 to < 18 years of age.
	With respect to the evaluation of efficacy, surrogate efficacy and safety of the single or repetitive intravenous infusions of BT524, each bleeding event (part II) will be considered as an individual case in the primary analysis.
Countries/ Number of Study Sites	5-7 sites in the European Union and in non-EU countries

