### Figure 1: ROTEM Readout of Citrated Normal Blood

The ROTEM® analyses: FibTEM® test (fibrin clot obtained by platelet inhibition with cytochalasin D). The clotting time (CT (seconds)) represents the time from the start of the test until a clot firmness of 2 mm is detected; maximum clot firmness (MCF (mm)) represents the total amplitude of the clot (Schochl et al. 2010).

In the ROTEM read out of Fib-tem S test expected reference (normal range) values for the amplitude of MCF are 9-25 mm for fibrinogen levels (PPD

In patients with congenital afibrinogenemia or severe congenital hypofibrinogenemia the MCF would not be measurable (refer to Figure 2):

Figure 2: Fib-tem S Readout in Afibrinogenemia

	00020 111 - 111 - 111	- - 11- 11-2-11-2-1-2-1-2-1-2-1-2-1-2-1-2-			
CALCULA MANDALO					
FIBT	ËM			2:	ar na sana sana na na n
FIBT CT:	EM 1855	CFT:	- 5	2: α:	

Sample collection and processing are described in the laboratory manual.

- 14.4.5.2 Methods for Assessing, Recording and Analyzing Clinical Efficacy Parameters
- 14.4.5.2.1 Investigator Assessment on Overall Hemostatic Response to Treatment with BT524

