5.6 Handling of MCF, Fibrinogen Activity and Fibrinogen Antigen values below detection limit

MCF (Maximum Clot Firmness) samples are analysed by central lab. Given that MCF values below the detection limit of “< 2mm” are indicated in the output of the testing as “not measurable”, it was discussed and decided in the BDRM (dated 25-Jun-2020) that for the purpose of the planned descriptive statistical analyses these values will be set to half of the range below the detection limit (range is “0 to 2”, i.e. value used is “1 mm”). In the listings of individual patient data, the MCF output “non measurable” will be presented as “< 2mm” (2 mm is the lower detection limit).

Fibrinogen Activity samples are analysed by local and central lab. Given that Fibrinogen Activity values below the detection limit are indicated by “<” sign before the lower detection limit in the output of the testing, it was discussed and decided that for the purpose of the planned descriptive statistical analyses these values will be set to half of the range below the detection limit.

Fibrinogen Antibody samples are analysed by central lab. Given that Fibrinogen Antibody values below the detection limit are indicated by “<” sign before the lower detection limit in the output of the testing, it was discussed and decided that for the purpose of the planned descriptive statistical analyses these values will be set to half of the range below the detection limit. For values indicated in the output of the testing as “<0.0” the value “0” will be used in the planned descriptive statistical analyses.

6 Patient Accounting and Disposition

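### The pre-dose MCF input to the only power statement (mean 4 mm, SD 7 mm) conflicts with the plan's own description of its patients, so the 80% needs restating with its assumptions

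*Protocol*

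**What the plan says.** Protocol 15.1, repeated in SAP 3.1, gives the trial's only formal sample-size calculation. The test is paired: "On the basis of a t-test assessing the difference between dependent means". The inputs are 15 patients, a "pre-treatment mean of 4 mm (SD 7 mm) and a post-treatment mean of 10 mm (SD 8 mm"), and a two-sided 5% level. The result is that "an effect size of 0.8 mm can be detected with a power of 80" per cent. Neither document gives a source for the means and SDs, a pre/post correlation, or an SD of the change. The 15 matches the synopsis, which enrols about 20 patients aged 6 or over "to have about 15 evaluable patients for the analyses of the PK/PD of BT524".

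Protocol 15.2 and SAP 5.1 make the 1-hour MCF change the only confirmatory test. SAP 10.2 limits it to patients aged 18 or over. Protocol 11.1.5 guarantees 10 adults in part I; patients 11 to 20 may be 6 to 75 years old.

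The protocol's MCF section (14.4.5.2.1, Figures 1 and 2) describes the untreated state: "In patients with congenital afibrinogenemia or severe congenital hypofibrinogenemia the MCF would not be measurable". It also says that "expected reference (normal range) values for the amplitude of MCF are 9-25 mm". SAP 5.6 says of results below the 2 mm detection limit that "these values will be set to half of the range below the detection limit (range is" 0 to 2 mm), so the value analysed is 1 mm.

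**The concern.** The patients in the power statement are the same patients whose MCF the protocol calls not measurable. Taken together, the MCF section and SAP 5.6 describe pre-dose values at or near a constant 1 mm, with little or no spread. The power statement gives those values a mean of 4 mm and an SD of 7 mm. This input enters the calculation twice: in the 6 mm difference (10 minus 4) and in the SD that turns 6 mm into 0.8. If it does not describe the patients, the printed 80% is not the power of the confirmatory test in them.

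Two further gaps sit in the same sentence. A paired calculation needs the SD of the change, or the correlation, and neither is given. The 0.8 is also printed in mm, although it works only as a standardised effect.

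**Working it through.** **Method.** Two-sided paired t-test, alpha 0.05, power from the noncentral t distribution with n−1 degrees of freedom and noncentrality d√n. Here d = mean change / SD of change, and SD of change = √(SD_pre² + SD_post² − 2ρ·SD_pre·SD_post).

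**1. The printed figure.** With d = 0.8 and n = 15, power is 82.1%, and 15 is the smallest n that reaches 80%. From the printed SDs, SD of change = √(49 + 64 − 112ρ) = √(113 − 112ρ). At ρ = 0.5 this is √57 = 7.55, so d = 6/7.55 = 0.795 and power is 81.6%. The figure therefore reproduces if ρ is about 0.5. Read literally as 0.8 mm, with ρ = 0.5, power would be 6.7%.

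**2. Dependence on the unstated correlation** (printed means and SDs, n = 15).

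| ρ | SD of change (mm) | d | Power |
|---|---|---|---|
| 0 | 10.63 | 0.564 | 53.0% |
| 0.3 | 8.91 | 0.673 | 67.9% |
| 0.5 | 7.55 | 0.795 | 81.6% |
| 0.7 | 5.88 | 1.020 | 95.6% |
| 0.9 | 3.49 | 1.718 | about 100% |

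**3. What mean 4, SD 7 requires.** For values between a floor a and a maximum M with mean m, the variance is at most (m − a)(M − m). Hence M ≥ m + SD²/(m − a).
- Floor 0 mm: M ≥ 4 + 49/4 = 16.25 mm.
- Floor 1 mm (SAP 5.6): M ≥ 4 + 49/3 = 20.3 mm.
- If 7 is read as the sample SD of 15 values, these become 15.4 and 19.2 mm.

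Some untreated patients would have to lie at these levels, inside the 9–25 mm reference range.

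**4. Power with pre-dose inputs closer to the plan's description.** Post-dose mean 10 (SD 8) is kept from the plan. The rows with measurable pre-dose values are assumptions, because the documents give no such figures.

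| Pre-dose | ρ | SD of change (mm) | d | Power, n=15 | Power, n=10 |
|---|---|---|---|---|---|
| all 1 mm | – | 8 | 9/8 = 1.125 | 98.1% | 88.5% |
| mean 2, SD 2 | 0 | √68 = 8.25 | 8/8.25 = 0.970 | 93.7% | 77.9% |
| mean 2, SD 2 | 0.5 | √52 = 7.21 | 8/7.21 = 1.109 | 97.9% | 87.6% |
| mean 3, SD 3 | 0 | √73 = 8.54 | 7/8.54 = 0.819 | 83.9% | 63.7% |
| mean 3, SD 3 | 0.5 | √49 = 7.00 | 7/7 = 1.000 | 94.9% | 80.3% |

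The coding constant matters little. If every pre-dose value were 0 mm or 2 mm instead of 1 mm, power at n = 15 would be 99.4% or 94.9%. For comparison, d = 0.8 at n = 10 gives 61.6%.

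**The case against.** The strongest reply is that the pre-dose figure is a planning assumption that can be met, and that nothing turns on it. Much of that stands.

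- A reader might infer that mean 4, SD 7 cannot occur. The documents do not go that far. It is possible within 0–25 mm. No eligibility criterion concerns MCF; inclusion criterion 2 admits fibrinogen up to 0.5 g/l, and no MCF value is given for that level. Figure 2, to which the not-measurable sentence refers, is titled for afibrinogenemia only. The qualifier after the 9–25 mm range is partly blacked out.
- A reader might infer an arithmetic error. There is none: 15 patients and 80% are right for a standardised effect of 0.8.
- The 1 mm rule was agreed in June 2020 for descriptive analyses, long after the planning figures were set. It shows how such values will be handled, not that the planners miscalculated.
- The post-dose mean 10 (SD 8) is just as unsourced, so any restated power is conditional on it.
- The primary objective is PK, which has no formal sample size.

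These points limit the wording and the urgency. They do not reconcile the two passages: one says that these patients have no measurable MCF, the other gives them a wide measurable distribution, and neither document explains the difference.

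**Conclusion.** The point holds as an inconsistency between the power statement and the plan's own description of its patients. The 80% is correct for its inputs but is not the power under that description, and it also rests on an unstated correlation of about 0.5.

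On the closest reading (all pre-dose values 1 mm, post-dose mean 10, SD 8), power is about 98% at n=15 and about 88% at n=10. A reader might infer that the trial is underpowered, but on this reading power is higher than printed. If some pre-dose values are measurable, for example mean 3, SD 3 with correlation 0 to 0.5, power is 84–95% at n=15 and 64–80% at n=10. How many adults supply data therefore matters as much as the pre-dose input.

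A reader might also keep the 6 mm change and use only the post-dose SD (6/8 = 0.75, 77% at n=15). That mixes incompatible inputs: the 6 mm exists only if the pre-dose mean is 4 mm, while an SD of change of 8 mm assumes that pre-dose values do not vary.

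**What to change.** In SAP 3.1, with a matching note to protocol 15.1:

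- Replace the pre-dose mean 4 mm (SD 7 mm) with an input that agrees with the MCF section and SAP 5.6, or give its source and explain the difference.
- State the mean change and the SD of the change (or the correlation) used.
- Give 0.8, if it is kept, as a standardised effect without a unit.
- Withdraw the unqualified 80%. State power as conditional on post-dose mean 10 mm (SD 8 mm): about 98% at n=15 and about 88% at n=10 if all pre-dose values are 1 mm.
- Add a sensitivity range for some measurable pre-dose values, such as the mean 3, SD 3 case above, at both sample sizes, because SAP 10.2 confines the confirmatory test to adults.

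The cost is one rewritten paragraph and a note, plus acknowledging that the planning input did not fit the population described. No patients, data or procedures change.

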#### 11.1.5 Enrolment Procedures

## With respect to safety, the following study-specific enrolment procedures are implemented in study part I:

The first five of the approximately 20 patients planned are to be recruited consecutively taken into account a dosing-free safety interval of 7 days between each patient.

The dosing-free safety interval of two expected biological half-lives of BT524 (according to the Core SmPC of Human Fibrinogen:  $t_{1/2}$  = 3-4 days) is considered to be sufficient for the detection of immediate (i.e., hypersensitivity) and later adverse effects (i.e., thrombosis).

Subsequently, patients 6 to 20 are allowed to be treated simultaneously, if applicable.

The first 10 of the approximately 20 patients planned are to be adults (aged 18 to 75 years). Patients 11 to 20 are allowed to be 6 to 75 years of age. A Data Monitoring Committee (DMC) has been established to assess the available adult safety- and PK-data prior to the enrolment of any children ( $\geq$  6 years) and adolescents into the study. Each patient is to be hospitalized until PK follow-up day 2 to ensure a close monitoring of the safety parameters and potential adverse effects.

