#### Planned enrolment of children and adolescents:

Patients 6 to 10 may then be treated simultaneously; again there will be a 7-day dosing-free safety interval after the 10th adult patient. After completion of patient 10, a DMC will review the available safety data prior to the enrolment of any children and adolescents into the study. Patients 11 to 20 are also allowed to be treated simultaneously, if applicable.

Subsequently, after the first 20 patients of  $\geq 6$  to  $\leq 75$  years finished part I, at least 3 additional paediatric patients < 6 years of age are planned to be enrolled in the study part I. Prior to enrolment of any children < 6 years of age a DMC will review and assess all available safety and PK/PD data from adults and children  $\geq 6$  years including data of at least 3 children  $\geq 6$  to < 12 years and of at least 3 adolescents  $\geq 12$  to < 18 years.

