### Part I

For analysis of PD, the same software will be used to determine the respective parameters with fibrinogen activity data.

Surrogate efficacy parameter MCF, assessed by fib-tem S, will be evaluated by a one sample t-test (pre-/post-comparison) and presented in a tabular format and/or graphical format. This analysis will be confirmatory for the 1 hour post-end of infusion assessment.

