2.1 Changes to the study protocol

The statistical analysis as specified in this SAP is consistent with the statistical analysis as specified in the study protocol (version 6.0).

In the study protocol age groups were defined to describe/define differences in time points of study assessments to be performed for different age groups (see flowchart of study in study protocol section 3). In the SAP age groups were defined differently for data analyses.

Shift tables specified in the study protocol for safety laboratory assessment will be not used.

No changes in the clinical study protocol were considered necessary by the Sponsor to handle clinical protocol deviations possibly related to the COVID-19 pandemic at the end of the study. It was therefore decided in the Blinded Data Review Meeting (BDRM) of June 25, 2020, that any non-conformities in the study conduct caused by the COVID-19 pandemic will be described in a note to file, and any COVID-19 related protocol deviation per patient will be listed in BDRM minutes and presented in study listings where appropriate.

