10.2 Secondary endpoint analyses of part I

PD parameters defined for the secondary objective will be derived from concentration-time profiles using adapted methodology, non-compartmental analysis, compartment analysis, or population modelling, as required. Details related to the analysis of these PD parameters will be specified in separate PK analyses plans.

In the scope of this SAP, descriptive summary statistics, including changes from baseline for the fibrinogen activity (from part I), will be provided for each age group (based on SAF, FAS, PP, and PK population). Values from each age group will be evaluated by a one-sample t-test (pre-/post-comparison) and presented in a tabular format. Surrogate efficacy parameter MCF, assessed by fib-tem S, will be measured in part I pre-dose and at 1 and 8 hours post-end of each IV infusion in patients \geq 6 years. MCF will be measured pre-dose and at 1 hour post-end of infusion in children between 2 and $<$ 6 years and pre-dose and at the end of each infusion in children $<$ 2 years.

Descriptive statistics including change from baseline will be presented for each age group, i.e. $<$ 2 years, 2 to $<$ 6 years, \geq 6 to $<$ 12 years, 12 to $<$ 18 years, \geq 18 years (based on FAS, PP, and SAF population).

Values for the patients \geq 18 years will be evaluated by a one-sample t-test (pre-/post-comparison) and presented in a tabular format.

This analysis, done for both post-dosing time points, will be considered confirmatory for the 1 hour post-end of infusion assessment in patients \geq 18 years. Additionally, 95%-confidence levels will be calculated.

More precisely, the t-test will assess the mean difference $\mu_{1,0}$ between dependent measurements (1h post minus pre-treatment MCF difference; one sample) and test the null hypothesis $H_0: \mu_{1,0} < 0$ versus the alternative $H_1: \mu_{1,0} > 0$ at a two-tailed α -level of 0.05.

Correlation between MCF and fibrinogen activity pre-dose and at 1 and 8 hours post-end of each IV infusion will also be assessed in patients ≥ 6 years.

Note that (according to protocol section 14.4.5.2.5) consumption of BT524 (dose per kilogram body weight and total dose) during part I, calculated and presented in the framework of exposure and compliance (cf. section above), can also be assessed and interpreted as efficacy endpoint in respect to MCF.

Also the efficacy parameter MCF will be presented as a whisker box plot for FAS.

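### The detectable MCF effect is printed as 0.8 mm but is a unitless standardised effect, and SAP 10.2 limits the confirmatory test to adults without declaring the change

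*Protocol*

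**What the plan says.** Protocol 15.1 sets out the sample-size calculation for MCF: "On the basis of a t-test assessing the difference between dependent means", post minus pre, in one sample. The inputs are 15 patients, a pre-treatment mean of 4 mm (SD 7 mm), a post-treatment mean of 10 mm (SD 8 mm) and two-sided alpha 0.05. The stated result is that "an effect size of 0.8 mm can be detected with a power of 80" per cent. SAP 3.1 repeats this, including the unit. Neither document gives the SD of the paired change or the pre/post correlation.

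The 15 patients are those in the protocol synopsis, where about 20 patients aged 6 to 75 "will be included to have about 15 evaluable patients for the analyses of the PK/PD of BT524 and the surrogate efficacy parameter". On adults, Protocol 11.1.5 requires only that "The first 10 of the approximately 20 patients planned are to be adults (aged 18 to 75 years"; patients 11 to 20 may be aged 6 to 75.

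For the test itself, Protocol 15.2.5 (Part I) says "This analysis will be confirmatory for the 1 hour post-end of infusion assessment" and sets no age limit. Protocol 15.2 and SAP 5.1 identify the same single confirmatory test, also without an age limit. SAP 10.2 runs the t-test in patients aged 18 or older and says it "will be considered confirmatory for the 1 hour post-end of infusion assessment in patients" of that age. SAP 2.1 declares: "The statistical analysis as specified in this SAP is consistent with the statistical analysis as specified in the study protocol (version 6.0". It then mentions differently defined age groups for data analyses, dropped shift tables and COVID-19 handling. Neither SAP 2.1 nor SAP 2.2 mentions a change of confirmatory population.

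**The concern.** A detectable effect of 0.8 mm cannot be squared with a planned change of 10 − 4 = 6 mm and SDs of 7 and 8 mm. Either the figure or its unit had to be wrong, and if the figure was wrong, the sample size might be wrong too. The input that would settle this, the SD of the paired change, is missing.

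The second problem concerns the same test. The 80% power was calculated for 15 evaluable patients aged 6 to 75, but the SAP tests adults only. The number of evaluable adults is not given and could be below 15. A reader relying on SAP 2.1 would not learn that patients under 18 have been removed from the only confirmatory test. The study is open-label and the SAP is dated July 2020, after the data review meeting of 25 June 2020. The documents do not show when the restriction was introduced. Nothing here shows that it was data-driven, but a stated reason is needed to close the question.

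**Working it through.** **Method.** Power is that of the one-sample t-test on the paired change, from the noncentral t distribution with n − 1 degrees of freedom and noncentrality d√n, at two-sided alpha 0.05. Here d = mean change / SD of change, and SD of change = √(7² + 8² − 2ρ·7·8) for pre/post correlation ρ. Since ρ is not stated, it is varied.

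**1. Reproducing n = 15.** Take 0.8 as unitless. At n = 15 the noncentrality is 0.8 × √15 = 3.10 and power is 82.1%. At n = 14 power is 79.0%. So 15 is the smallest n that reaches 80%, and the plan's sample size reproduces.

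**2. Taking 0.8 mm literally.**

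| ρ | SD of change (mm) | d = 0.8 / SD | Power, n = 15 | n for 80% power |
|---|---|---|---|---|
| 0 | 10.63 | 0.075 | 5.9% | 1388 |
| 0.5 | 7.55 | 0.106 | 6.7% | 701 |
| 0.9 | 3.49 | 0.229 | 13.1% | 152 |

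For 0.8 mm to reach 80% power with 15 patients, ρ would have to be about 0.9995.

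**3. What 0.8 implies.**
- SD of change = 6 / 0.8 = 7.5 mm, so ρ = (49 + 64 − 56.25) / 112 = 0.507.
- If 0.8 is rounded from 0.75: SD 8.0 mm, ρ 0.44, power 77.1% at n = 15.
- If 0.8 is rounded from 0.85: SD 7.1 mm, ρ 0.56, power 86.4%.
- Dividing 6 mm by the pooled SD √(113/2) = 7.52 mm also gives 0.798.
- The unstated correlation matters: at ρ = 0, d = 6 / 10.63 = 0.564, power at n = 15 is 53%, and 27 patients would be needed.

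**4. Adult-only test at d = 0.8.**

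| Evaluable adults | 10 | 11 | 12 | 13 | 14 | 15 |
|---|---|---|---|---|---|---|
| Power | 62% | 67% | 71% | 75% | 79% | 82% |

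Ten is the number of adults the protocol requires. Before any child under 6 is enrolled, the data monitoring committee reviews the accumulated data, "including data of at least 3 children" aged 6 to under 12 and at least 3 adolescents (Protocol 11.1.5). If all six are among the roughly 20 part I patients (an assumption), at most about 20 − 3 − 3 = 14 are adults.

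**5. A more favourable case.** The text introducing Figure 2 of the protocol says MCF would not be measurable in this population, and SAP 5.6 sets values below 2 mm to 1 mm. Assume every pre-dose value is 1 mm with SD near 0, and post-dose is 10 mm with SD 8 mm. Then d = 9 / 8 = 1.125, and power is 98% with 15 patients and 88.5% with 10.

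**The case against.** The strongest reply is that the first half is editorial. Effect size usually means a standardised quantity, both means and SDs are printed beside it, and n = 15 reproduces. That stands as far as the sample size goes. The sentence is still false as written in two documents, and the printed SDs yield 0.8 as a paired effect only with an unstated correlation near 0.5.

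On the restriction, SAP 10.2 states the adult limit openly, SAP 2.1 mentions different age groups, and the protocol leaves efficacy detail to the SAP. But a remark about age groups for data analyses does not tell a reader that everyone under 18 has left the confirmatory test. Scheduling does not explain the cut-off either: only children under 2 lack a 1-hour part I sample.

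On power, the adult count is unknown, ten is a minimum, the ceiling of 14 is an assumption, 79% is close to nominal, and the floor scenario gives 88.5% with ten adults. All of this stands and limits the claim: the stated power is not assured for the adult-only test, which is different from saying the test is underpowered.

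A last objection is that requiring both a pre-dose and a 1-hour value is narrower than the protocol's ITT and PP populations, which allow last-observation-carried-forward where appropriate, and would admit ages 2 to under 6. A paired test needs both values, and the protocol's wording sets no lower age limit, so this does not defeat the option. MCF is a secondary surrogate; the PK objective is unaffected.

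**Conclusion.** Both parts hold. The unit in Protocol 15.1 and SAP 3.1 is wrong: 0.8 works only as a unitless standardised effect, corresponding to a 6 mm change with an SD of about 7.5 mm (7.1 to 8.0 mm if 0.8 is rounded). The sample size of 15 does not change.

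The adult-only confirmatory test in SAP 10.2 departs from Protocol 15.2.5 and is not declared in SAP 2.1. For that test the 80% power is not assured: at d = 0.8 it runs from 62% with 10 evaluable adults to 79% with 14. These figures rest on the plan's own 0.8 and on an adult count the documents do not give; power would be higher if most pre-dose values sit at the 1 mm floor. This should be corrected, but it does not invalidate the design.

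**What to change.** In both documents, replace the power sentence with:

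> With 15 evaluable patients, a mean MCF increase of 6 mm (standardised effect 0.8, no unit) is detected with about 80% power at two-sided alpha 0.05.

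The sponsor should add the SD of the paired change that it actually assumed.

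Then do one of the following in the SAP:

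- **(a)** Restore the protocol's population for the confirmatory test in 10.2: part I patients with a pre-dose and a 1-hour value, no age limit.
- **(b)** Keep the adult-only test, list the restriction and its reason in SAP 2.1, and add to SAP 3.1:

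> The 80% power applies to 15 evaluable patients aged 6 to 75 years; at standardised effect 0.8 it is lower for the adult-only test if fewer than 15 adults are evaluable (about 62% with 10).

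The cost is one corrected sentence per document and one disclosed SD, plus either a changed population in SAP 10.2 or one added line each in SAP 2.1 and 3.1. Sample size is unchanged. Option (a) brings paediatric values into the confirmatory test; option (b) means conceding that 80% power is not assured for it.
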